7. CLINICAL STUDY REPORT APPENDICES

7.1. SAS Codes

7.1.1. SAS codes to impute the missing using MCMC MI

***** Bulbar Conjunctival Hyperemia multiple imputations *****;
 ***** Photographic Assessments *****;

```
PROC MI DATA=pr1t SEED=738493 OUT=pr1miyp MINIMUM=0 MAXIMUM=4 ROUND=1 NIMPUTE=25;
  MCMC INITIAL=EM;
  by PARAMN PARAMCD;
  where SEFL="Y" and PARAMCD in ("BCHSCTP" "BCHSCFP" "BCHSCNP");
  /* TRTPN_FG1 TRTPN_FG2 are dummy variables based on TRTPN*/
  VAR TRTPN_FG1 TRTPN_FG2 AVAL2 AVAL4;
RUN;
***** Investigator Assessments *****;
PROC MI DATA=pr1t SEED=738493 OUT=pr1miyi MINIMUM=0 MAXIMUM=4 ROUND=1 NIMPUTE=25;
  MCMC INITIAL=EM;
  by PARAMN PARAMCD;
  where SEFL="Y" and PARAMCD in ("BCHSCTI" "BCHSCFI" "BCHSCNI");
  VAR TRTPN_FG1 TRTPN_FG2 AVAL2 AVAL3 AVAL4 AVAL5 AVAL6 AVAL7;
RUN;
```

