4.2.9.1. Imputation Method for Primary Efficacy Endpoints

To impute missing, Markov Chain Monte Carlo (MCMC) multiple imputation (MI), Fully Conditional Specification multiple imputation (FCS MI) and LOCF methods will be used.

For MI, we will have below phases:

1. Imputation Phase: in this phase, the missing data will be imputed using SAS PROC MI and a complete data set will be created. This process of imputation will be repeated 25 times. Therefore, 25 compete datasets will be created. In this phase, treatment group, baseline value, and post-baseline visits will be included in multiple imputation model.
2. Analysis Phase: each of the 25 complete data sets will be analyzed independently using desired statistical method (e.g. ANCOVA for primary efficacy analysis).
3. Pooling Phase: in this phase the estimates obtained from each analyzed complete dataset from phase 2, will be combined using PROC MIANALYZE.

The primary analyses of efficacy data will use MCMC MI methodology to impute missing data. The expectation and maximization (EM) algorithm will be used to estimate the mean vector and the covariance assuming a missing at random (MAR) distribution. The MAR distribution assumes the probability that a value is missing does not depend on the true values of the missing items. The imputation phase will create 25 copies of the dataset which will contain different estimates of the missing values. The 25 complete datasets will then be analyzed to produce several sets of parameter estimates and standard errors, which will then be pooled to create a single set of results.

Last observation carried forward (LOCF) method and Fully Conditional Specification multiple imputation (FCS MI) with 200 burn-in iterations and 25 times of imputation under the assumption of missingness at random will be used for sensitivity analyses (Section 4.7.2).

Sponsor:	Ocular Therapeutix, Inc.		
Protocol:	OTX-DED-2020-201		
Document Version No.:	V1.0	Document Date:	11NOV2021

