4.7.1. Primary Analyses

For the primary efficacy endpoint analyses of change from baseline in photographic assessment of bulbar conjunctival hyperemia (evaluated by central reading center) worst zone in the study eye at Visit4 (Day 15) (as defined in section 2.6.1.1), the following modeling and analyses will be performed on mITT population, observed data:

An analysis of covariance (ANCOVA) model will be run to estimate least square (LS) means treatment. This model will include the baseline value as a covariate for adjustment and treatment group as the sole factor. Least square means will be used to make treatment comparisons using Dunnett's adjustment for multiple comparisons to a control. Statistical significance of treatment differences will be determined using a two-sided significance level of $\alpha = 0.05$.

In the ANCOVA model, LS means treatment group comparison of OTX-DED 0.2 mg to HV, OTX-DED 0.3 mg to HV, and Overall OTX-DED (combined OTX-DED 0.2 mg and OTX-DED 0.3 mg using sample size weights of OTX-DED 0.2 mg and OTX-DED 0.3 mg groups as coefficients for the parameters) to HV will be reported. Unadjusted treatment group analyses using two-sample t-test and Wilcoxon rank sum test will be run on these treatment group combinations.

Each bulbar conjunctival hyperemia zone (Nasal, Temporal, and Frontal) and the Total of the three zones in study eye will be analyzed in a manner similar to the primary efficacy variable as described above.

The same analyses will be done for the non-study eye. For non-study eye, the worst zone similar to worst zone in study eye (details in section 2.6.1.1) will be independently determined using photographic assessment bulbar conjunctival hyperemia in non-study eye at baseline.

Sponsor:	Ocular Therapeutix, Inc.		
Protocol:	OTX-DED-2020-201		
Document Version No.:	V1.0	Document Date:	11NOV2021

The primary efficacy endpoints will also be analyzed on PP population.

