4.7.2. Sensitivity Analyses

To determine robustness of results, the sensitivity analyses will be performed for the primary efficacy endpoint, bulbar conjunctival hyperemia at Visit4 (Day 15), on the mITT and PP populations by using:

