1. MCMC MI
2. last observation carried forward (LOCF)
3. FCS MI.

As sensitivity analyses, LOCF will be analyzed in a manner similar to the primary efficacy variable (details in section 4.7.1). MCMC MI and FCS MI will be analyzed in a manner similar to the primary efficacy variable (details in section 4.7.1), however, for treatment comparisons, least square means will not be adjusted for multiple comparison and for the unadjusted treatment group comparisons, only t-test will be used.

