7.1.2. SAS codes to impute the missing using FCS MI

***** Bulbar Conjunctival Hyperemia multiple imputations *****;
 ***** Photographic Assessments *****;

```
PROC MI DATA=pr1t SEED=918411 OUT=pr1fchyp MINIMUM=0 MAXIMUM=4 ROUND=1 NIMPUTE=25;
  by PARAMN PARAMCD;
  where SEFL="Y" and PARAMCD in ("BCHSCTP" "BCHSCFP" "BCHSCNP");
  class TRTPN;
  VAR TRTPN AVAL2 AVAL4;
  fcs nbiter=200 reg (AVAL2=TRTPN);
  fcs nbiter=200 reg (AVAL4=TRTPN AVAL2);
RUN;
***** Investigator Assessments *****;
PROC MI DATA=pr1t SEED=918411 OUT=pr1fcysi MINIMUM=0 MAXIMUM=4 ROUND=1 NIMPUTE=25;
  by PARAMN PARAMCD;
  where SEFL="Y" and PARAMCD in ("BCHSCTI" "BCHSCFI" "BCHSCNI");
  class TRTPN;
  VAR TRTPN AVAL2 AVAL3 AVAL4 AVAL5 AVAL6 AVAL7;
  fcs nbiter=200 reg (AVAL2=TRTPN);
  fcs nbiter=200 reg (AVAL3=TRTPN AVAL2);
  fcs nbiter=200 reg (AVAL4=TRTPN AVAL3);
  fcs nbiter=200 reg (AVAL5=TRTPN AVAL2 AVAL3 AVAL4);
  fcs nbiter=200 reg (AVAL6=TRTPN AVAL2 AVAL3 AVAL4 AVAL5);
  fcs nbiter=200 reg (AVAL7=TRTPN AVAL2 AVAL3 AVAL4 AVAL5 AVAL6);
RUN;
```

Sponsor:	Ocular Therapeutix, Inc.		
Protocol:	OTX-DED-2020-201		
Document Version No.:	V1.0	Document Date:	11NOV2021

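### Both multiple-imputation checks on the Day-15 photograph repeat the primary estimate by construction, so their agreement with it is not evidence of robustness

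*SAP*

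**What the plan says.** - **Primary.** SAP 4.7.1: "the following modeling and analyses will be performed on mITT population, observed data". On the ANCOVA: "This model will include the baseline value as a covariate for adjustment and treatment group as the sole factor". SAP Section 5 explains that the protocol's MCMC-imputed primary was replaced because it could not be combined correctly with Dunnett's adjustment.
- **Sensitivity analyses.** SAP 4.7.2: "To determine robustness of results, the sensitivity analyses will be performed for the primary efficacy endpoint". The methods are MCMC MI, LOCF and FCS MI. For the two MI analyses, "least square means will not be adjusted for multiple comparison".
- **Imputation models for the photograph.** SAP 7.1.1 (MCMC) lists "VAR TRTPN_FG1 TRTPN_FG2 AVAL2 AVAL4". SAP 7.1.2 (FCS) uses "fcs nbiter=200 reg (AVAL4=TRTPN AVAL2", closing the list there. AVAL2 and AVAL4 are the Visit 2 (Day 1) and Visit 4 (Day 15) grades.
- **Assumption.** SAP 4.2.9.1 fits the MCMC model "assuming a missing at random (MAR) distribution" and specifies 25 FCS imputations "under the assumption of missingness at random will be used for sensitivity analyses". It also promises to include post-baseline visits. Photographs are scheduled only at baseline and Day 15 (Protocol Appendices 1 and 6), so for this endpoint the promise reduces to the missing value itself.
- **Related data.** The investigator hyperemia grade is scheduled at every visit. Early leavers are asked to complete the Visit 7 assessments (Protocol 7.6.2; Appendix 1, footnote 6), which include that grade but no photograph (Protocol 8.4.7). SAP 7.1.1 imputes the investigator grades in a model of their own. They do not enter the photographic one.

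Neither document plans a delta-adjusted, tipping-point or control-based analysis.

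**The concern.** An mITT subject without a Day-15 photograph drops out of the primary. Failed insertions in the study eye are already outside mITT, and leaving after Day 15 does no harm, so the subjects in question are those lost before Day 15 or attending without a usable photograph. A robustness check should ask what happens if they did better or worse than treatment and baseline predict. An imputation built on treatment and baseline gives them that same prediction, with noise. A report would then show a primary and two MI results in close agreement, and a reader would take this as support. If loss is related to outcome differently in the two arms, all three carry the same bias. SAP 4.1 says the trial is to supply estimates for later designs, so an empty assurance could be carried forward.

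**Working it through.** The plan gives no loss rate, effect size or SD, so there is no figure to reproduce. Rates and effects below are assumed.

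**1. Algebra.** Let X hold intercept, treatment and baseline, and let c be the change to Day 15. The primary solves X_obs′(c_obs − X_obs b) = 0, giving b̂. Regressing the Day-15 grade on the same X gives the same fit, with the baseline slope larger by 1. Averaged over many imputations, the missing changes become X_mis b̂. Refitting on everyone solves X_obs′(c_obs − X_obs b) + X_mis′(X_mis b̂ − X_mis b) = 0. Both terms vanish at b = b̂, so MI returns the primary estimate.

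Numerical check (one zone, no bounds, 150 subjects, 15 missing): primary −0.45298751 and −0.39713981, MI limit identical. With 25 imputations the Monte Carlo SD was 0.008 against an SE of 0.119. Over 5% to 30% missing it was 0.004 to 0.017 against 0.12 to 0.14.

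**2. As coded.** This simulation used 50 per arm, whole grades 0–4, imputation by zone, rounding, 25 imputations and then the worst baseline zone, with a true difference of about −0.4 and 5%, 10% or 20% missing. MI minus primary averaged 0.000 to +0.006 grade. The 95th percentile of the absolute gap was 0.019 to 0.058 and the correlation 0.979 to 0.998, against an SE of 0.14 to 0.16.

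**3. P-values.** With 150 − 4 = 146 degrees of freedom, the critical t is 1.976 unadjusted and 2.231 with Dunnett. Two unadjusted comparisons have a familywise error of about 0.090. A smaller MI p-value is therefore not added support.

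**4. Size of the shared bias.** Let p be an arm's loss rate and d the mean excess of its missing Day-15 grades over the MAR prediction. Then bias (OTX-DED minus HV) = p_HV × d_HV − p_OTX × d_OTX. Equal loss rates protect only if d is also equal.

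A second simulation had 1,500 replicates per scenario, overall OTX-DED vs HV, full-data SE 0.126, and d of 0.54 to 0.60 where loss was outcome-related. LOCF was taken as zero change. Negative bias overstates benefit.

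| Loss HV/OTX-DED, outcome-related in | Observed | MI as coded | LOCF | LOCF − observed |
|---|---|---|---|---|
| 10%/10%, none (random) | −0.001 | +0.001 | +0.038 | +0.039 |
| 10%/10%, all arms | 0.000 | +0.002 | +0.040 | +0.040 |
| 10%/10%, OTX-DED only | −0.058 | −0.057 | −0.014 | +0.044 |
| 10%/10%, HV only | +0.058 | +0.059 | +0.092 | +0.034 |
| 12%/5%, all arms | +0.037 | +0.035 | +0.012 | −0.025 |
| 5%/12%, all arms | −0.039 | −0.034 | +0.054 | +0.093 |
| 20%/8%, all arms | +0.062 | +0.058 | +0.010 | −0.052 |
| 8%/20%, OTX-DED only | −0.110 | −0.102 | +0.055 | +0.165 |

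Check on row 3: 0.10 × (−0.01) − 0.10 × 0.57 = −0.058. The largest bias is 0.110/0.126 = 0.87 SE; the next is 0.062/0.126 = 0.49 SE. With one arm affected, a bias of one SE needs d = 0.126/p: 2.52, 1.26 or 0.63 grade at 5%, 10% or 20% loss.

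**5. Using the investigator grade.** In row 3, the Visit 2 grade alone removed 2% of the MI bias. A post-baseline or exit grade for half / all leavers removed 5% / 9% at partial correlation 0.23, 16% / 29% at 0.42 and 34% / 63% at 0.62. In step 2's simulation, where missingness was driven by that grade and arm (the case that most favours it), the shares at 5%, 10% and 20% missing were 0.025/0.030 = 83%, 0.055/0.059 = 93% and 0.102/0.110 = 93%.

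**6. Delta adjustment.** In row 3, adding 0.6 grade to imputed OTX-DED values only brought the bias to +0.004; adding it in all arms left −0.057. Under random loss, adding it to OTX-DED only moved the estimate by +0.061. Delta must therefore differ by arm, and its range must include 0.

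**The case against.** The strongest reply is that the planned set does not rest on MI alone. LOCF departs from MAR, and in the two largest-bias scenarios it visibly leaves the primary: by 0.165 grade (0.165/0.126 = 1.3 SE) at 8%/20% and by 0.052 at 20%/8%. At 10%/10%, where it stays closer, the bias is at most 0.058. The trial is unpowered and descriptive, and every loss rate here is assumed. The imputation code follows SAP 4.2.9.1, and a delta analysis cannot detect outcome-related loss either.

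Most of this stands and limits the point. A reader might infer that the plan has no departure from MAR, or that the whole sensitivity set is empty; LOCF contradicts both. A reader might also infer that missing photographs would go unreported. SAP 4.2.1 already gives n by treatment group and visit, and SAP 4.4 gives reasons for withdrawal by arm.

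What LOCF does not do is show how the result depends on the assumption in each arm. At 10%/10% it sat 0.034 to 0.044 above the primary under all four mechanisms, while the true bias ran from −0.058 to +0.058. It moved by +0.039 even when loss was random and the primary unbiased.

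**Conclusion.** The point holds for the two MI analyses of the Day-15 photograph. They use the primary's variables under MAR, so their point estimates repeat the primary up to small noise and cannot corroborate it. This follows from the SAP text and code and needs no assumed loss rate.

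The consequence is less certain. A reader might infer that the primary is materially biased, but the documents give no loss rate and no evidence that loss depends on outcome. The 0 to 0.11 grade range rests on assumed losses of 5% to 20%, a difference of about −0.40 and d of about 0.6 where loss is outcome-related. Its upper end needs 20% loss in OTX-DED, outcome-related in that arm only. With few missing photographs all methods agree. The severity is minor because the trial is descriptive, but the remedy is cheap.

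**What to change.** In the SAP, before unmasking:

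1. Add the investigator hyperemia grades, at least Visits 2 to 4 and any early-exit grade, to the photographic MCMC and FCS models. State which visit an exit grade is assigned to, since SAP 4.2.10 uses nominal visits and does not settle this. State whether zone or overall grades are used: Protocol Appendix 5 describes an overall rating, while SAP 2.6.1.2 and 4.7.3 use zones. Zone grades would have to be merged by zone, because the code runs by parameter. The gain depends on correlation and availability and may be small.
2. Alongside LOCF, add one delta-adjusted (tipping-point) MI for the Day-15 photograph, with delta varied separately for OTX-DED and HV over a range that includes 0. Say that it displays dependence on the assumption and does not detect outcome-related loss. State that LOCF carries the baseline photograph forward.

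The cost is some extra programming, the two placement rules, one more table and a delta range to justify. The primary analysis and the study procedures do not change.

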7.1.2. SAS codes to impute the missing using FCS MI

***** Bulbar Conjunctival Hyperemia multiple imputations *****;
 ***** Photographic Assessments *****;

```
PROC MI DATA=pr1t SEED=918411 OUT=pr1fchyp MINIMUM=0 MAXIMUM=4 ROUND=1 NIMPUTE=25;
  by PARAMN PARAMCD;
  where SEFL="Y" and PARAMCD in ("BCHSCTP" "BCHSCFP" "BCHSCNP");
  class TRTPN;
  VAR TRTPN AVAL2 AVAL4;
  fcs nbiter=200 reg (AVAL2=TRTPN);
  fcs nbiter=200 reg (AVAL4=TRTPN AVAL2);
RUN;
***** Investigator Assessments *****;
PROC MI DATA=pr1t SEED=918411 OUT=pr1fcysi MINIMUM=0 MAXIMUM=4 ROUND=1 NIMPUTE=25;
  by PARAMN PARAMCD;
  where SEFL="Y" and PARAMCD in ("BCHSCTI" "BCHSCFI" "BCHSCNI");
  class TRTPN;
  VAR TRTPN AVAL2 AVAL3 AVAL4 AVAL5 AVAL6 AVAL7;
  fcs nbiter=200 reg (AVAL2=TRTPN);
  fcs nbiter=200 reg (AVAL3=TRTPN AVAL2);
  fcs nbiter=200 reg (AVAL4=TRTPN AVAL3);
  fcs nbiter=200 reg (AVAL5=TRTPN AVAL2 AVAL3 AVAL4);
  fcs nbiter=200 reg (AVAL6=TRTPN AVAL2 AVAL3 AVAL4 AVAL5);
  fcs nbiter=200 reg (AVAL7=TRTPN AVAL2 AVAL3 AVAL4 AVAL5 AVAL6);
RUN;
```

Sponsor:	Ocular Therapeutix, Inc.		
Protocol:	OTX-DED-2020-201		
Document Version No.:	V1.0	Document Date:	11NOV2021

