7.1.3. SAS codes to run ANCOVA (using PROC MIXED) on MI data

```

*** MULTIPLE IMPUTATIONS ***;
*** PROC MIXED ***;
ods output LSMESTIMATEs=outlsmean0(rename=(label=PARAMETER));
proc mixed data=din;
  by AVISIT PARAMN INPUT;
  CLASS TRTPN (ref=last);
  MODEL CHG=TRTPN BASE;
  LSMESTIMATE TRTPN "OTX-DED 0.2MG" 1 0 0,
    "OTX-DED 0.3MG" 0 1 0,
  /* WG1 and WG2 are the sample size weighted coefficient for group 1 and 2 respectively*/
    "Overall OTX-DED" &WG1. &WG2. 0,
    "HV" 0 0 1,
    "OTX-DED 0.2MG vs HV" 1 0 -1 ,
    "OTX-DED 0.3MG vs HV" 0 1 -1 ,
    "Overall OTX-DED vs HV" &WG1. &WG2. -1 / cl;
  run;

ods output ParameterEstimates=outlsmean1;
PROC MIANALYZE DATA=outlsmean0;
  modeleffects estimate;
  stderr stderr;
  by avisit PARAMN PARAMETER;
RUN;

```

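### The FCS code for the investigator-rated Day 15 redness grade leaves out the baseline grade, against the SAP text, its sister models and the ANCOVA it feeds (minor; one term to add)

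*SAP*

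**What the plan says.** SAP 4.2.9.1 describes the imputation phase as follows: "treatment group, baseline value, and post-baseline visits will be included in multiple imputation model". That section is headed for primary endpoints. SAP 4.7.3 and SAP 5 extend the same sensitivity analyses (MCMC MI, LOCF, FCS MI) to the investigator assessment of hyperemia, whose main analysis uses observed data.

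The printed code for the investigator grade, by visit:

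- Visit 3, FCS: "fcs nbiter=200 reg (AVAL3=TRTPN AVAL2"
- Visit 4 (Day 15), FCS: "fcs nbiter=200 reg (AVAL4=TRTPN AVAL3"
- Visit 5, FCS: "fcs nbiter=200 reg (AVAL5=TRTPN AVAL2 AVAL3 AVAL4"; Visits 6 and 7 follow the same pattern, with AVAL2 present
- All visits, MCMC (SAP 7.1.1): "VAR TRTPN_FG1 TRTPN_FG2 AVAL2 AVAL3 AVAL4 AVAL5 AVAL6 AVAL7"

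The photographic (primary) Day 15 grade has its own FCS line, with baseline: "fcs nbiter=200 reg (AVAL4=TRTPN AVAL2". The imputed data then go into an ANCOVA of change from baseline (SAP 7.1.3): "MODEL CHG=TRTPN BASE".

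AVAL2 is the Visit 2 (Day 1) grade. Photography is scheduled only at Visits 2 and 4, and its code uses only AVAL2 and AVAL4.

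**The concern.** One line out of five post-baseline lines in the block drops baseline, and the SAP gives no reason. It looks like a slip, not a choice. Three things follow.

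- Text and code disagree, so a programmer who follows one departs from the other.
- The analysis model conditions on baseline while the model that generates the missing outcome does not. The imputed Day 15 grades therefore carry too weak a relation to baseline. SAP 4.2.9.1 rests FCS on missingness at random; for this visit the code narrows that to missingness explained by treatment and the Visit 3 grade.
- FCS and MCMC are run side by side as checks on robustness. With different predictors at Day 15, a disagreement between them could not be put down to the method alone.

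Imputed AVAL4 is also a predictor for Visits 5 to 7, so some distortion could carry forward within the same FCS analysis. That was not quantified.

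**Working it through.** **What the documents supply.** They give the code, the ANCOVA and 50 subjects planned per arm. They give no effect size, SD, between-visit correlation or missing-data rate, and no figure for this point, so there is nothing of the plan's own to reproduce.

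**Assumed inputs.** True active-minus-HV difference −0.30 at Visit 3 and −0.50 at Day 15; SD 0.7; equal between-visit correlation of 0.5 to 0.7; 10–25% missing at Day 15, with 30% of those also missing at Visit 3.

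**Step 1: the baseline slope, by hand.** Take correlation 0.6, equal SDs and 20% missing completely at random.

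- Correct slope of change on baseline: 0.6 − 1 = −0.40.
- A Day 15 value imputed from Visit 3 alone is tied to baseline only through Visit 3: 0.6 × 0.6 = 0.36, so its slope is 0.36 − 1 = −0.64. The same holds when Visit 3 was itself imputed from baseline.
- Mixed: 0.8 × (−0.40) + 0.2 × (−0.64) = −0.448.

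The simulation below gives −0.448.

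**Step 2: the treatment difference.** Simulated FCS step followed by the ANCOVA, 20,000 per arm, correlation 0.6, 20 replicates, 3 imputations. The Monte Carlo standard error of the estimates with AVAL2 omitted is 0.001 to 0.002.

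| Day 15 missingness depends on | Missing | Difference, AVAL2 omitted | Difference, AVAL2 included | Slope, omitted | Slope, included |
|---|---|---|---|---|---|
| nothing | 20% | −0.501 | −0.502 | −0.448 | −0.400 |
| arm | 20% | −0.500 | −0.499 | −0.447 | −0.400 |
| Visit 3 grade | 24% | −0.497 | −0.498 | −0.466 | −0.406 |
| baseline, alike in all arms | 24% | −0.500 | −0.501 | −0.486 | −0.400 |
| baseline, HV only | 21% | −0.462 | −0.499 | −0.460 | −0.400 |
| baseline, active arms only | 23% | −0.539 | −0.501 | −0.474 | −0.401 |

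Treatment is in the line, so each arm keeps its own level. If redder subjects drop out, their imputed grades come out too low. When this happens equally in all arms the error cancels in the difference; when it happens in one arm type it does not, and its sign depends on which. The shifts are 0.499 − 0.462 = 0.037 toward zero and 0.539 − 0.501 = 0.038 away from it.

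**Step 3: at the trial's size.** 50 per arm, correlation 0.5, 25 imputations, 400 replicates.

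- Standard error with 20% missing at random: 0.141 omitted against 0.136 included; 0.141 / 0.136 = 1.037. Across the six mechanisms at 20–24% missing the increase is about 4%; at 10–14% missing it is 2–3%.
- Mean shift: 0.0385 toward zero (HV only) or 0.0382 away (active only). With a standard error of 0.139, the first is 0.0385 / 0.139 = 0.28 standard errors.
- In a single trial the two versions differ by chance with an SD of about 0.03, in either direction.

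**Step 4: the discrete scale.** With grades rounded to 0–4 (5,000 per arm, correlation 0.6), the shifts are 0.042 toward zero and 0.043 away under the two arm-specific mechanisms, and at most 0.002 under the other three mechanisms run.

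**The case against.** **Scope.** The line feeds one of three sensitivity analyses of a secondary endpoint, in a trial that SAP 4.1 calls unpowered and descriptive. A baseline-inclusive analysis under missingness at random already exists for this endpoint in the MCMC code. All of this stands and sets the severity.

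**The text.** SAP 4.2.9.1 is headed for primary endpoints and also names post-baseline visits. Adding AVAL2 still leaves out AVAL5 to AVAL7, which the MCMC model uses. That is fair, but every FCS line in the block uses only treatment and earlier visits; the Visit 4 line alone among the post-baseline lines omits baseline. The conflict with the ANCOVA does not depend on how 4.2.9.1 is read.

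**A stronger reading.** A reader might infer that the omission shrinks the treatment effect, or biases it whenever missingness relates to baseline redness. One can build such a case: with missingness rising with baseline redness in the vehicle arm only, the estimate shrinks by 5–9%, or by 12–19% if baseline predicts Day 15 better (0.6) than Day 8 does (0.4). The documents do not say that missingness behaves this way. The mirror-image assumption moves the estimate the other way, and equal dependence in all arms leaves it unbiased. With those second correlations (baseline–Day 8 0.3, Day 8–Day 15 0.4, baseline–Day 15 0.6; 60,000 per arm), omission gave −0.440 for HV only, −0.577 for active only and −0.498 for all arms alike, against −0.512, −0.507 and −0.499 with baseline included. No fixed direction is supported.

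**Conclusion.** Wrong as written, minor severity. The omission and its conflict with the SAP text, the sister models and the ANCOVA can be read off the page and rest on no assumption. The consequences are a distorted outcome–baseline relation in the imputed data (slope −0.45 to −0.49 instead of −0.40 at correlation 0.6), a small loss of precision, and a possible bias of about 0.04 on a difference of 0.50, of either sign, only under arm-specific dependence of missingness on baseline. These sizes rest on assumed correlations, effect and missing-data rates; the absence of a fixed direction held in every setting run. Calling the FCS analysis invalid as a robustness check would go too far: outside that one kind of missingness it estimates the treatment difference essentially without bias. The primary endpoint is not touched.

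**What to change.** In SAP 7.1.2, investigator block, change the Visit 4 line to `fcs nbiter=200 reg (AVAL4=TRTPN AVAL2 AVAL3);`. With that term the simulated difference returns to about −0.50 under all six mechanisms. It needs no new data and no design change, and no downside was found.

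The appendix prints FCS code for hyperemia only, while SAP 4.7.3 also applies FCS to the eye dryness scores and corneal staining. Check those programs for the same slip. If the line was left out on purpose, the SAP should say so and give the reason.
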